4.4 Packaging and Labeling of Study Drugs

Drugs will be packaged and labeled per UCSF institutional standards, adhering to applicable local and federal laws.

5 Treatment Plan

5.1 **Dosage and Administration**

Treatment will be administered on an outpatient basis.

Table 5.1 Regimen Description

Study Drug	Dose	Route	Schedule	Cycle Length
Ruxolitinib	20mg or 15mg dependent on baseline	РО	BID	Pre-operative window (14-21 days) or up to 28 days for delayed
	platelet count			surgery

5.2 Dose De-escalation Rule

A continuous monitoring rule for safety will be instituted, to guard against excess toxicity from pre-operative treatment with ruxolitinib at the FDA-indicated starting dose for patients with myelofibrosis (20 mg bid for patients with a platelet count \geq 200,000 or 15 mg bid for patients with a platelet count \geq 150,000 and < 200,000). See section 8.3.3 Safety Lead-In

Table 5.2 below describes the number of toxicity events per number of treated patients required to trigger the ruxolitinib de-escalation rule. Table 8 also shows the posterior probability that the rate exceeds 33%, and the binomial probability associated with the decision for an assumed

Phase 2 - Ruxolitinib Page 30 of 67

33% discontinuation rate. The prior probability has a beta distributions with parameters a = 1 and b = 9, assumes a 10% mean with an approximate 80% mid-range of .0 to .22.

Table 5.2 Boundaries for the De-Escalation Rule

Participants	Treatment-Related Discontinuations	PP(π > 33%)*	$Pr(X \ge r p = .33)$
6	5	.629	.017
8	6	.685	.019
11	7	.673	.037
14	8	.664	.054
17	9	.657	.071
20	10	.650	.087
23	11	.645	.101
27	12	.594	.145
30	13	.592	.156
33	14	.590	.167

 $^{^*\}pi$ is the discontinuation rate. The minimum acceptable upper bound of a treatment-related discontinuation is 33%. PP(π > 33%) is the posterior probability that the discontinuation rate exceeds this 33% upper bound. This posterior probability of discontinuation is calculated from the prior distribution, the number of participants treated and the observed number of treatment-related discontinuations.

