8.2.3 Safety Lead-in

A continuous monitoring rule for safety will be instituted, to guard against excess toxicity from pre-operative treatment with ruxolitinib at the FDA-indicated starting dose for patients with myelofibrosis (20 mg bid for patients with a platelet count \geq 200,000 or 15 mg bid for patients with a platelet count \geq 150,000 and < 200,000). The first cohort of 6 patients will be treated at this starting dose. After enrollment of the 6th patient, we will continuously monitor the number of

Phase 2 - Ruxolitinib Page 49 of 67

patients who discontinue ruxolitinib and come off study for ruxolitinib-attributable toxicity. A qualifying toxicity must be at least possibly related to ruxolitinib, as judged by the treating investigator, and fulfill one of the following definitions:

- Grade ≥ 3 non-hematologic toxicity, with the exception of asymptomatic electrolyte abnormalities manageable with repletion.
- Intolerable non-hematologic toxicities of any grade, which persist despite optimal medical management.
- Grade ≥ 3 thrombocytopenia or neutropenia.

If the posterior probability of \geq 33% toxicity rate exceeds 50% for patients having to discontinue window treatment due to qualifying toxicity, this would be considered unacceptable and would result in de-escalating the starting dose of ruxolitinib to 10 mg p.o. bid, the FDA-indicated starting dose in polycythemia vera, for all subsequent patients. This would be the starting dose in all patients with a qualifying platelet count for this study (\geq 150,000), including those with platelet count \geq 150,000 and < 200,000 and those with platelet count > 200,000. (see section 5.2 Dose De-Escalation Rule)

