3.1 Adverse Event Monitoring

All Grade 3-5 Adverse Events (AEs), regardless of being unexpected or considered to be associated with the use of the study drug will be entered into OnCore®, UCSF's Clinical Trial Management System.

Adverse Events are graded according to the Common Terminology Criteria for Adverse Events (CTCAE) as developed and revised by the Common Therapy Evaluation Program (CTEP) of the National Cancer Institute. Adverse Events are further given an assignment of attribution or relationship to treatment or medical procedure. Attribution categories are:

- **Definite** The adverse event is clearly related to the investigational agent(s) or medical procedure.
- Probable The adverse event is likely related to the investigational agent(s) or medical procedure.
- Possible The adverse event may be related to the investigational agent(s) or medical procedure.
- Unlikely The adverse event is doubtfully related to the investigational agent(s) or medical procedure.
- Unrelated the adverse event is clearly not related to the investigational agent(s) or medical procedure.

All Grade 3-5 adverse events entered into OnCore® will be reviewed on a monthly basis at the UCSF Site Committee meetings. All adverse events entered into OnCore® will be reviewed on a monthly basis at the UCSF Coordinating Center Site Committee meetings. All clinically significant adverse events must be reported to the UCSF Coordinating Center by the participating sites within 10 business days of becoming aware of the event or during the next scheduled monthly conference call, whichever is sooner. The UCSF Site Committee will review and discuss the selected toxicity, the toxicity grade, and the attribution of relationship of the adverse event to the administration of the study drug(s) from the UCSF Coordinating Center and the participating sites.

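### The de-escalation rule counts patients still inside their treatment window as having tolerated the drug, so it can fire late, by about one to two patients at the faster accrual

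*Combined protocol and SAP*

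**What the plan says.** Section 5.2 (Dose De-escalation Rule) gives the denominator twice. It introduces the boundaries with "Table 5.2 below describes the number of toxicity events per number of treated patients required to trigger the ruxolitinib de-escalation rule", and the footnote to Table 5.2 says "This posterior probability of discontinuation is calculated from the prior distribution, the number of participants treated and the observed number of treatment-related discontinuations". On the prior it states "The prior probability has a beta distributions with parameters a = 1 and b = 9". The limit is a 33% discontinuation rate, and under section 8.2.3 (Safety Lead-in) the rule fires when the posterior probability of reaching that rate exceeds 50%.

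Section 8.2.3 also fixes when the looks begin: "After enrollment of the 6th patient, we will continuously monitor the number of" patients coming off for ruxolitinib-attributable toxicity. The starting point is enrollment of patient 6, not the end of that patient's window. Treatment lasts 14-21 days, or up to 28 if surgery is delayed (section 5.1).

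No passage restricts the count to finished windows, weights patients still on drug, or pauses enrollment while outcomes are pending.

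On reporting, Appendix 2, section 3.1 asks participating sites to send clinically significant adverse events to the coordinating center "within 10 business days of becoming aware of the event or during the next scheduled monthly conference call, whichever is sooner". Appendix 2, section 3.2 allows 1 business day for serious adverse events.

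**The concern.** A beta-binomial posterior assumes that every patient in the denominator has a known outcome. A patient on day 2 has not yet had the chance to discontinue, but as worded adds one to the denominator and nothing to the numerator. With the number of events fixed, every pending patient lowers the posterior. The direction of the bias therefore needs no assumption; only its size does.

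The rule sets the starting dose for all later patients, so its value lies in firing before more of them start. A late signal means that a few more patients begin at a dose the plan's own criterion would already have called unacceptable.

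Reporting time can add to this. Qualifying toxicity includes grade 3 or higher thrombocytopenia or neutropenia, and intolerable non-hematologic toxicity of any grade. Neither has to be serious, so such an event at a participating site may fall under the longer reporting limit.

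**Working it through.** **1. Reproduce Table 5.2.** With r discontinuations among n treated, the posterior is Beta(1 + r, 9 + n − r), and the tabulated value is P(π > .33). All ten posteriors and all ten binomial tails in the table reproduce to three decimals (5 of 6: .629 and .017; 14 of 33: .590 and .167). One event fewer at each listed n gives a posterior below .50, so each boundary is the smallest that fires. The table's arithmetic is correct.

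**2. Add pending patients.**

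| Discontinued | Known outcome | Pending | n used | Posterior | Fires? |
|---|---|---|---|---|---|
| 5 | 6 | 0 | 6 | .629 | yes |
| 5 | 6 | 1 | 7 | .558 | yes |
| 5 | 6 | 2 | 8 | .489 | no |
| 6 | 10 | 0 | 10 | .556 | yes |
| 6 | 10 | 1 | 11 | .492 | no |

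For example, 5 of 8 gives Beta(6, 12).

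**3. How many patients are pending?** Planned enrollment is 45 (section 3.2).
- Over the 12-month enrollment period of section 8.2.4: 45/12 = 3.75 per month. The expected number on drug is 3.75 × 14/30.4 = 1.7 to 3.75 × 28/30.4 = 3.5.
- Over the 24 months to primary completion (section 3.6.1): 45/24 = 1.9 per month, giving 0.9 to 1.8 on drug.

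**4. Simulated delay.** Assumptions not in the documents: Poisson accrual, windows uniform on 14-22 days, discontinuation times spread evenly over the window, a look at every start and every resolved outcome, and no reporting lag. Ranges span independent sets of 700 to 1,500 simulated trials; with 1,500 trials the Monte Carlo error on a percentage is about one point.

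| Assumed true rate 50% | As written | Time-weighted |
|---|---|---|
| 3.75/month: fires by 11th start | 26-29% | 36-38% |
| 3.75/month: fires by 20th start | 63-65% | 70-73% |
| 3.75/month: mean started when it fires | 18.8-19.1 | 16.9-17.8 |
| 1.9/month: mean started when it fires | 17.3 | 16.6 |

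The rule eventually fires in about 96-98% of trials under either denominator. At true rates of 10-20% it fires in 0-3% under either.

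Other settings agree. With 2 per month and 21-day windows, time weighting moves the mean number treated from 22.2 to 21.3 at a true rate of 45%, and from 11.7 to 11.3 at 60%. With 3.9 per month and 28-day windows, it moves from 24.6 to 22.5 and from 13.7 to 12.4.

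**5. Reporting lag, worst case.** Ten business days is about 14 calendar days. Applying that lag to every event in the trial, at 3.75 per month and a true rate of 50%, raises the mean number started from 19.1 to 22.8. This is an upper limit, because the 10-day maximum does not apply to coordinating-center patients or to serious events.

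**6. Price at the limit itself.** At a true rate of 33% and 3.75 per month, the chance of firing by the 20th start goes from about 13-15% to 18-19% with time weighting; a smaller set of 700 trials put the difference at about one point. Across the accrual and window settings run, the overall chance of firing rises from about .34-.37 as written to .42-.45 if only completed or discontinued patients are counted.

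**The case against.** The sponsor can fairly say that the effect is small and the example extreme. Five toxicity discontinuations in six patients is far from the prior mean of 10%, and section 5.5 expects few if any hematologic abnormalities. Each patient with a qualifying grade 3-4 toxicity comes off drug under section 5.5 whatever this rule does. All of that stands. It limits the size of the point but does not supply a missing definition, and the rule exists for the case where the expectation of low toxicity fails.

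On reporting, the 10 business days is a maximum from a general multicenter monitoring plan and applies to participating sites only. Section 7.6 has weekly committee review of adverse events, section 9.6 asks for case report forms as soon as possible after the visit, and Appendix 2, section 2 gives the Study Chair continuous review of data and safety. Section 7.3.2.3 names blood dyscrasias among events that may be judged serious, which would carry the 1-business-day limit. A reader might infer that the lag defeats continuous monitoring for the whole trial; given these routes, the documents do not support that.

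Two other strong readings also fail. Table 5.2 is not miscalculated. Nor does any single pending patient silence the rule: 5 of 7 still fires, although 6 of 11 does not.

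Time weighting is imperfect too. The calendar in section 6.1 schedules one on-treatment clinical blood draw, within 5 days before surgery. Weighting by days on drug would therefore credit a mid-window patient with hematologic tolerance that nobody has measured.

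**Conclusion.** The point holds as a modest weakness that is cheap to repair. The stated denominator treats unresolved patients as successes, and two pending patients are enough to turn a firing result into a non-firing one at the first boundary. At an assumed true rate of 50%, the cost is about 1-2 extra patients started at 3.75 per month and under 1 at 1.9 per month. At true rates of 20% or less the choice hardly matters. The reporting limit is a secondary contributor with a worst case confined to participating sites and events not judged serious.

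The direction is certain. The size rests on the assumed true rate, accrual, window length and evenly spread event times. Hematologic events found only at the pre-surgery draw would surface later than assumed and lengthen the delay.

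A reader might infer that the rule fails to protect patients. The documents do not support that: it still fires in nearly all simulated trials when the true rate is 50%, and individual stopping does not depend on it.

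**What to change.** - **Sections 5.2 and 8.2.3:** define the denominator as patients who completed the window or discontinued for qualifying toxicity, plus each ongoing patient weighted by the fraction of a fixed reference window completed. State the reference length, because planned treatment varies from 14 to 28 days. If preferred, give no credit for hematologic toxicity beyond the last blood test. A simpler alternative is to count completed plus discontinued patients only.
- **Appendix 2, section 3.1:** require any discontinuation that counts toward the rule to reach the coordinating center within 1 business day, the timeline already used for serious events.
- **Leave unchanged:** the prior, the 33% limit, the 50% criterion and the dose action.

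The cost is a wording amendment and a short spreadsheet formula. With weighting, the count is no longer a whole number, so the posterior is read from the formula and not from Table 5.2. The rule will also fire slightly more often at a true rate of 33%, by the amounts in step 6 of the working; the sponsor should accept that openly when choosing between the two denominators.

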5.3 Procedures in Case of Overdose

There are no known antidotes for ruxolitinib. The treatment of AEs associated with overdose should be supportive for the underlying adverse symptoms.

Single doses up to 200 mg have been given with acceptable acute toxicity. Doses of study treatment in excess of that specified (20 mg twice daily) in the clinical study protocol are considered to be an overdose. Overdose, with or without associated symptoms, should be handled in the same way as a SAE. Signs or symptoms of an overdose that meet the criteria of SAE should be reported as a SAE in the appropriate manner and be documented as clinical sequelae to an overdose.

5.4 **Procedures in Case of Pregnancy**

Pregnancy in itself is not regarded as an AE unless there is a suspicion that an investigational product may have interfered with the effectiveness of a contraceptive treatment. All reports of congenital abnormalities/birth defects are SAEs. Any SAE experienced during pregnancy must be reported on the SAE Report Form. Elective terminations for medical reasons, and any serious complications of pregnancy (including spontaneous miscarriage) should be reported as SAEs. Elective abortions without complications should not be handled as SAEs.

The time period for collecting information on the occurrence of a pregnancy is from first administration of study treatment up to and including the follow up period. The outcome of all pregnancies (spontaneous miscarriage, elective termination, normal birth or congenital abnormality/birth defects) must be followed up and documented even if the participant was discontinued from the study.

Phase 2 - Ruxolitinib Page 31 of 67

5.5 **Dose Modifications and Dosing Delays**

The following dose modification rules will be used with respect to potential toxicity. Toxicity will be assessed according to the NCI Common Terminology Criteria for Adverse Events Version 4.0 (CTCAE v4.0).

Ruxolitinib is approved for use in myelofibrosis at the dose of 20 mg po bid when the baseline platelet count > 200,000, 15 mg po bid when the baseline platelet count is > 100,000 but \leq 200,000, and 5 mg bid when the baseline platelet count is > 50,000 but \leq 100,000. Ruxolitinib is approved in polycythemia vera at the dose of 10 mg po bid.

Dose reductions will not be allowed. Treatment delays up to 1 week are permitted as follows:

- If participants experience any grade 3-4 ruxolitinib-related non-hematologic toxicities in the neo-adjuvant window, the study drug will be discontinued and they will be removed from the study. (Exception: Patients with asymptomatic grade 3 electrolyte abnormalities manageable with repletion) Patients may also be removed from study for intolerable non-hematologic toxicities of any grade, which persist despite optimal medical management.
- If participants experience grade ≥ 3 thrombocytopenia or neutropenia, ruxolitinib will be discontinued and they will be removed from the study.
- Grade 3 anemia does not require discontinuation from protocol. Patients may be transfused per discretion of the treating physicians.
- For mild or moderate (grade 1 or 2) side effects that are difficult to tolerate, treatment
 may be held for up to 1 week. Treatment may be resumed at the same dose, if there is
 improvement by at least one grade. Dose delays more than 1 week will not be permitted.
 If treatment is restarted, study physicians should aim for at least 3 days of ruxolitinib
 exposure prior to planned surgery.

In two Phase 3 clinical studies of ruxolitinib in myelofibrosis, the median time to onset of first CTCAE grade two or higher anemia was 6 weeks, and approximately 8 weeks until onset of grade 3 or 4 thrombocytopenia. In nearly all cases, ruxolitinib-induced anemia and thrombocytopenia could be reversed with dose reduction or interruption; occasionally red blood cell or platelet transfusions were required. Thus, given the short 2-3 weeks of treatment during this study, it is expected that few, if any, participants will develop hematologic abnormalities. Moreover, participants in the current study do not have a primary bone marrow malignancy which is the target of ruxolitinib and thus predisposes to hematologic toxicity. Any participants that experience anemia or thrombocytopenia may be transfused if deemed necessary by the treating physician.

Although clinically significant hematologic and non-hematologic toxicity is unexpected during the 14-21 days of protocol treatment in patients with operable HNSCC, a continuous monitoring rule for excess toxicity will be instituted. Please see Section 5.6 below.

5.6 **Monitoring and Toxicity Management**

Each patient receiving ruxolitinib will be evaluable for safety. The safety parameters include all laboratory tests and hematological abnormalities, physical findings, and spontaneous reports of adverse events reported to the investigator by patients.

Each patient will be assessed periodically for the development of any toxicity as outlined in Section 6 Study Procedures and Observations. Toxicity will be assessed according to the NCI

Phase 2 - Ruxolitinib Page 32 of 67

CTCAE v4.0. Dose adjustments will be made according to the system showing the greatest degree of toxicity.

We will monitor for the following anticipated adverse events:

Anemia

In the two Phase 3 clinical studies, median time to onset of first CTCAE Grade 2 or higher anemia was approximately 6 weeks. One patient (0.3%) discontinued treatment because of anemia. In patients receiving ruxolitinib, mean decreases in hemoglobin reached a nadir of approximately 1.5 to 2.0 g/dL below baseline after 8 to 12 weeks of therapy and then gradually recovered to reach a new steady state that was approximately 1.0 g/dL below baseline. This pattern was observed in patients regardless of whether they had received transfusions during therapy.

In the randomized, placebo-controlled study, 60% of patients treated with Jakafi and 38% of patients receiving placebo received red blood cell transfusions during randomized treatment. Among transfused patients, the median number of units transfused per month was 1.2 in patients treated with ruxolitinib and 1.7 in placebo treated patients.

Thrombocytopenia

In the two Phase 3 clinical studies, in patients who developed Grade 3 or 4 thrombocytopenia, the median time to onset was approximately 8 weeks. Thrombocytopenia was generally reversible with dose reduction or dose interruption. The median time to recovery of platelet counts above 50 X 10⁹/L was 14 days. Platelet transfusions were administered to 4.7% of patients receiving ruxolitinib and to 4.0% of patients receiving control regimens. Discontinuation of treatment because of thrombocytopenia occurred in 0.7% of patients receiving ruxolitinib and 0.9% of patients receiving control regimens. Patients with a platelet count of 100 X 10⁹/L to 200 X 10⁹/L before starting ruxolitinib had a higher frequency of Grade 3 or 4 thrombocytopenia compared to patients with a platelet count greater than 200 X 10⁹/L (16.5% versus 7.2%).

Neutropenia

In the two Phase 3 clinical studies, 1.0% of patients reduced or stopped ruxolitinib because of neutropenia.

Table 5.6 provides the frequency and severity of clinical hematology abnormalities reported for patients receiving treatment with Jakafi or placebo in the placebo-controlled study.

Table 5.6 Worst Hematology Laboratory Abnormalities in the Placebo-controlled Studya

	Jal	kafi (N=155)		Placebo (N=151)			
Laboratory Parameter	All Grades ^b (%)	Grade 3 (%)	Grade 4 (%)	All Grades (%)	Grade 3 (%)	Grade 4 (%)	
Thrombocytopenia	69.7	9.0	3.9	30.5	1.3	0	
Anemia	96.1	34.2	11.0	86.8	15.9	3.3	
Neutropenia	18.7	5.2	1.9	4.0	0.7	1.3	

a Presented values are worst Grade values regardless of baseline

Phase 2 - Ruxolitinib Page 33 of 67

b National Cancer Institute Common Terminology Criteria for Adverse Events, version 3.0

Additional Data from the Placebo-controlled Study

25.2% of patients treated with ruxolitinib and 7.3% of patients treated with placebo developed newly occurring or worsening Grade 1 abnormalities in alanine transaminase (ALT). The incidence of greater than or equal to Grade 2 elevations was 1.9% for ruxolitinib with 1.3% Grade 3 and no Grade 4 ALT elevations.

17.4% of patients treated with ruxolitinib and 6.0% of patients treated with placebo developed newly occurring or worsening Grade 1 abnormalities in aspartate transaminase (AST). The incidence of Grade 2 AST elevations was 0.6% for ruxolitinib with no Grade 3 or 4 AST elevations.

16.8% of patients treated with ruxolitinib and 0.7% of patients treated with placebo developed newly occurring or worsening Grade 1 elevations in cholesterol. The incidence of Grade 2 cholesterol elevations was 0.6% for ruxolitinib with no Grade 3 or 4 cholesterol elevations.

6 Study Procedures and Observations

The study-specific procedures and assessments are outlined in the Study Calendar – Section 6.1

Screening assessments must be performed within 28 days prior to the first dose of investigational product. Any results falling outside of the reference ranges may be repeated at the discretion of the investigator.

All on-study visit procedures are allowed **a window of ±5 days** unless otherwise noted. Treatment or visit delays for public holidays or weather conditions do not constitute a protocol violation.

Phase 2 - Ruxolitinib Page 34 of 67

6.1 **Study Calendar**

Table 6.1 Schedule of Study Procedures and Assessments

Study Procedures	Screening	Treatment Period			Surgery		Final study
		Days 1 thru 14 to 21	Days 22 thru 28 (if surgery is delayed)	Pre-surgery visit (within 5 days prior to surgery)	(between 14-28 days of ruxolitinib start) ⁹	4-week post-op visit	visit (12-week post- op)
Informed Consent	Х						
History and Physical Examination ^a	x			X		х	x
Vital Signs, Weight	Х			X		Х	X
ECOG-PS	Х			X		Х	Х
Pregnancy Test ^b	Х						
EKG ^c	Х						
Clinical Blood Testsd	Х			X		Х	Х
Cross-sectional imaging studye	х			Х			
Research Blood Collection ^h	х			Х			
Ruxolitinib ^f		х	Х	X (take until morning of surgery)			
Surgery ^g					Х		
Tumor sample ⁱ	Х				Х		
Archival tissue collection	Х						

a. History and physical examination within 8 weeks prior to study entry. This should include surgical assessment of the primary tumor, including fiberoptic nasopharyngoscopy or examination under anesthesia as indicated per standard of care, and as determined by the treating surgeon. Patients will be reevaluated within 5 days prior to scheduled surgery. Toxicity and compliance as evidenced by pill count and patient diaries will be assessed.

Phase 2 - Ruxolitinib Page 35 of 67

b. Pre-menopausal women of childbearing potential (WOCBP) must have a negative urine or serum pregnancy test within 4 weeks of registration. A negative pregnancy test must then be documented within 72 hours of Day 1 of ruxolitinib treatment.

c. The standard of care EKG performed for pre-surgical evaluation should be used. EKGs performed within 12 weeks prior to study entry may be substituted, provided the patient has experienced no interval cardiac event.

- d. Clinical blood tests include CBC with differential (to include total white blood cell count, absolute neutrophil count, hemoglobin, hematocrit and platelets), serum chemistries (to include sodium, potassium, chloride, HCO₃, BUN, creatinine, glucose, magnesium and calcium), liver function tests (to include total bilirubin, AST, ALT, total protein, albumin and alkaline phosphatase), coagulation studies (PT/INR and PTT), and C-reactive protein (CRP). Clinical blood tests will be repeated once within 5 days prior to surgery, and at the 4-week and 12-week post-operative visits if clinically indicated according to the investigator.

 Coagulation studies are not required at the 4 week or 12 week post-surgical visits.
- e. Within 6 weeks of study entry (within 4 weeks preferred), and again within 5 days prior to planned surgery, patients will undergo cross-sectional radiological evaluation using diagnostic contrasted CT, PET/CT (with diagnostic contrasted CT), or MRI of regions with radiologically or clinically identifiable tumor. The minimum cross-sectional evaluation is a diagnostic, contrasted computed tomography (CT) scan of the neck. PET/CT is the preferred modality, **provided it includes a diagnostic, contrasted CT scan of the neck** however is not mandatory. For patients with severe allergy to iodinated contrast dye despite premedication, or in the case of physician preference, neck MRI may be substituted. The pre- and post-treatment imaging modality should be the same, i.e. if MRI was used at study entry, it should be used at the post-treatment, pre-surgical assessment. **NOTE**: in the event that a patient lacks a CT-measurable primary tumor or metastatic lymph node, measurable disease may also be established by caliper measurement of an oral cavity or oropharyngeal tumor (≥ 1 centimeter). In this case, caliper measurement should be repeated within 5 days prior to planned surgery.
- f. The first day of ruxolitinib treatment will be considered Day 1. Ruxolitinib will be administered at 20 mg po bid, for 1421 days, and will be discontinued on the day of surgical resection (following the morning dose). If surgery is delayed, the study drug may be continued until surgery, for a maximum of 28 days. The interval between the last dose of ruxolitinib and surgery will be 2-24 hours.
- g. Surgery will be scheduled during days 14-21 of ruxolitinib treatment. For logistical reasons, surgery may be delayed by up to 7 days. Postoperative complications, hospital days, and ICU days will be noted for each patient.
- h. Research blood samples will be obtained at screening and within the 5 days prior to scheduled surgery. One (1) purple top EDTA tube will be collected at each time point. Please refer to the laboratory SOPs for processing instructions.
- i. Archival tissue if available. If no archival tissue is available participants must undergo tissue biopsy at baseline. Research biopsies obtained at screening during planned surgery for resection of the tumor will be divided into fresh, fresh-frozen and paraffin specimens.
- j. Patients will be seen for a standard 4 week post-operative visit (+/- 2 weeks), and again for a standard 12-week post-operative visit (+/- 4 weeks). Clinical blood tests will be obtained as deemed clinically necessary. Thereafter, patients will be followed off study per standard of care.

Phase 2 - Ruxolitinib Page 36 of 67

